3.5.4.2 Physical examinations

A physical examination including pulse rate and blood pressure will be performed according to the Visit Schedule. Information about the physical examination must be present in the source documentation at the study site.

There is no CRF to capture routine normal findings from physical examinations assessments. Data on concomitant diseases will not be captured on the CRFs.

3.5.4.3 Performance status and body weight

Measurements of performance status and body weight will be performed according to the Visit Schedules. The ECOG Performance Status Scale will be used in this study.

3.5.5 Quality of Life

Quality of life (QoL) will be measured at baseline and at the follow-up according to the Visits schedule. The EuroQol (EQ)-5D instrument will be used (http://www.euroqol.org/).

The patient is requested to fill the EQ-5D instrument prior to attending the treating physician, preferable at home in tranquil surroundings. The EQ-5D instrument is available in different languages, and the instrument written in the native language of the patient should be used.

3.5.6 Toxicity reporting

As there is no study drug, toxicity reporting is not relevant to the study. The adverse effects related to imatinib prior to study entry will be collected on the CRFs, and the study patients will be monitored for persistence/disappearance of the adverse effects during the study.

As far as possible, adverse event grade 1-4 will be described by the NCI/NIH Common Terminology Criteria for Adverse Events (CTCAhE) version 4.0 using severity grades 1-5 (http://ctep.cancer.gov/protocolDevelopment/electronic_applications/ctc.htm).²⁹

The severity grade of an adverse event provides a qualitative assessment of the extent or intensity of an adverse event, as determined by the investigator or as reported by the patient. The severity grade does not reflect the clinical seriousness of the event, only the degree or extent of the affliction or occurrence (e.g. severe nausea, mild seizure), and does not reflect the relationship to study drug.

Severity grade for events not listed in the NCI/NIH CTCAE v.4.0

- 1 =Grade 1 Mild
- 2 = Grade 2 Moderate
- 3 =Grade 3 Severe
- 4 = Grade 4 Life-threatening
- 5 = Grade 5 Death

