STUDY RATIONALE	Patients with metastatic GIST are currently recommended to have life-long treatment with tyrosine kinase inhibitors (TKI). The standard first-line treatment is imatinib, which is switched to other drugs at progression or if the patient does not tolerate imatinib. The prevailing hypothesis is that imatinib and other TKIs fail to completely eradicate metastatic GIST and that progression is inevitable if imatinib treatment is discontinued. However, the SSGXVIII/AIO trial found that 3 years of adjuvant imatinib yielded both superior RFS and OS rates compared to 1 year of adjuvant imatinib, which finding does not exclude the hypothesis that sufficiently long administration of imatinib might sometimes eradicate subclinical GIST. Furthermore, a few retrospective studies have reported favorable survival outcomes with surgery of residual disease in metastatic GIST in patients responding to imatinib, and a subset (approximately 20%) of patients with advanced GIST do not progress within the first 10 years on imatinib. Imatinib treatment comes with potential side- effects and, as of now, considerable costs to the society. Therefore, discontinuation of imatinib in highly selected patients, i.e. those who have received imatinib for longer than 5 years and who have undergone metastasectomy of all macroscopic oligometastatic disease, needs to be explored as a novel treatment strategy. Discontinuation might lead to detection of durable complete remissions without imatinib or even cure.
TARGET GROUP	Patients treated with imatinib longer than 5 years for oligo- metastatic GIST (\leq 3 metastases) and who have no longer detectable GIST lesions on CT/MRI imaging following complete surgical resection (R0/R1-resection) or RFA of the metastases.
END POINTS	 Primary: Three-year progression-free survival (PFS) after discontinuation of imatinib. Secondary: Overall survival Quality of life Exploratory: Plasma ctDNA as a liquid biopsy in follow-up Histologic and molecular genetics evaluation of excised tumor tissue Changes in the blood cell counts and blood biochemistry after stopping imatinib (includes hematology, serum transaminases, electrolytes, creatinine, creatinine kinase)

TRIAL DESIGN	An open-label, 1-group, prospective, multicenter phase II trial.	

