	 deficiency. 4. Presence of neurofibromatosis-1. 5. R2 resection of the primary tumour or metastasis. 6. Patient with inability to grant reliable informed consent. 7. Inability to comply with the scheduled follow-up. 8. Progressive disease during imatinib or other systemic treatments for GIST before or after surgery/REA of the
STUDY TOEATMENT	metastases. Study group: Discontinuation of imatinib
STUDI IREATMENT	No imatinib or other anti-cancer treatment will be administered.
ASSESSMENTS:	 Primary: Progression-free survival (PFS) is defined by the time interval between the date of imatinib discontinuation and the date of first detection of GIST progression or death, whichever occurs first. Patients alive without progression are censored on the date of last follow-up Secondary:
	 Overall survival (the time period between the date of imatinib discontinuation and the date of death). Quality of Life (EQ-5D instrument).
	 Exploratory: To explore the relationship between study endpoints and blood biomarkers including, but not limited to, KIT/PDGFRA mutations in cell-free circulating DNA in plasma and circulating growth factor and cytokine levels. To explore the relationships between study endpoints and biomarkers in resected tumors prior to study entry. Changes in the blood cell counts and blood biochemistry after stopping imatinib as compared to the values on

	imatinib (includes comparisons in blood cell counts, serum transaminases, creatinine, and electrolytes between the baseline values measured on imatinib and the values measured at 2, 5 and 8 months after stopping imatinib).		
Pre-planned interim analysis:			
	• 1-year PFS in the first 15 patients included. The study is		
	terminated if 10 or more of the 15 patients (≥ 67 %) have		
	progression of disease or withdraws from the study within		
	the first 12 months from the date of study entry.		
STATISTICAL	This is a superiority study as compared with historical controls		
CONSIDERATIONS	regarding the main endpoint (PFS). Based on historical data,		
	discontinuation of imatinib in patients with metastatic GIST is		
	associated with rapid recurrence/progression. In the BRF-14		
	study where patients were randomised to discontinue imatinib at		
	1 and 3 years on treatment, the 2-years PFS was 10 % and 16 %,		
	respectively. Based on these observations, the historical 3-year		
	PFS can be assumed to be 15 %. An improvement in 3-year PFS		

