	from 15 % to 35 % is considered as clinically significant. To find		
	this effect with 80% power using a one-sided statistical		
	significance level of 0.05 , 26 patients are needed. To allow a		
	drop-out rate of 15 %, 31 patients will be included in the trial		
	(power 0.8, one-sided alpha 0.05).		
	-		

Protocol Version Log

Protocol version (date)	Substantial amendment	Changes	Section
V1.0 (13Jun2016)	NA	NA	
V2.0	NA	New Project Manager contact	Contact Details
(24Oct2016)		Addition of Signature Page	Signature Page
		Additional section with potential risks and benefits	3.5.8
V3.0 (20Dec2016)		Added SSG and OUS logo, in addition to EudraCT number and ClinicalTrials.gov identifier	Front page
		Creatinin Kinase deleted	Protocol Synopsis
		Radiological central review included	3.5.3 Tumour assessments and 6 Central Radiological Review
		Adverse Event grade 1-2 included.	3.5.6 Toxicity reporting
V4.0	No	Changed protocol ID / title from "SSG	Front page
(15Mar2017)		XXIV: The Stop-GIST trial" to "SSG XXV: The Stop-GIST trial"	Synopsis
V5.0	Yes	Defined End of Study	3.4.5 End of study
(24Aug2017)		Specified that all amendments to the protocol should also be submitted to competent authorities	11.1.1 Changes to the protocol
		Added Monitoring Plan as appendix I	13 Appendix I

	Screening/ Baseline	Study group					Follow-up (study arm)								
Months from		2	5	8	11	15	19	23	27	31	36	42	48	54	60
randomisation															
Informed consent (a)	0 to -14 d														
Inclusion/ exclusion criteria	0 to -14 d														
Medical history &	0 to -14 d														
demographics (b)															
Regular medication (c)	0 to -14 d														
Adverse events (d)	0 to -14 d														
Physical examination (e)	0 to -14 d	х	Х	х	х	х	х	х	х	х	х	х	х	х	Х
Weight	0 to -14 d	х	Х	х	х	х	х	х	х	х	х	х	х	х	Х
Height	0 to -14 d														
ECOC performance status	0 to -14 d	х	Х	х	х	х	х	х	х	х	х	х	х	х	Х
Haematology (f)	0 to -14 d	х	Х	х	х	х	х	х	х	х	х	х	х	х	Х
Blood biochemistry (g)	0 to -14 d	х	х	х	х	х	х	х	х	х	Х	х	х	х	Х
CT/MRI of the abdomen &	0 to -28 d	х	х	х	х	х	х	х	х	х	Х	х	х	х	Х
pelvis (h)															
Quality of life (i)	0 to -7 d		Х		х		х		х		х		х		Х
Research plasma & serum (j)	0 to -7 d	х	Х	х	х	х	х	х	х	х	х	х	х	х	Х
Research blood (k)	0 to -7 d	X													
Resected metastatic tumour tissue collection (l)						X									

Visit schedule and assessments (Table 1)

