- (a) Written informed consent must be signed and dated by the patient prior any study-specific procedures. The centre must keep a log of the patients who received the informed consent.
- (b) Includes age, gender, race, date of first GIST histological diagnosis; As far as possible following should be collected: surgical margin, tumour size (cm), location, rupture, mitotic count (per 50 HPFs); date of starting imatinib; dose of imatinib (the highest and the lowest daily doses given for a period longer than 1 week), interruptions of imatinib dosing lasting longer than 2 weeks; major side-effects of imatinib recorded (grade 1- 4). As far as possible location of metastases (liver or peritoneal cavity), type of resection of metastases (R0 or R1), date of metastasis surgery if done, date of RFA if done, size of metastases (tumour longest diameter in centimetres), pathological response to treatment (complete/partial pathological response) should be collected.
- (c) Daily imatinib dose in milligrams before discontinuation.
- (d) Adverse events of imatinib at the time of study entry. Collected according to the CTCAE v.4.0.
- (e) Includes blood pressure and pulse rate.

- (f) Includes haemoglobin, total WBC count, platelet count, and a differential count including neutrophils, lymphocytes, monocytes, eosinophils and basophils. In the event that haematology evaluation has been performed within 14 days prior to the date of study inclusion, these tests do not need to be repeated.
- (g) Includes serum or plasma creatinine; serum total bilirubin, ALT, AST, alkaline phosphatase. LDH, albumin, calcium, magnesium and phosphate at follow-up months 2 and 5. In the event that blood biochemistry evaluation has been performed within 14 days prior to the study entry, these tests do not need to be repeated at screening.
- (h) Done with a contrast agent if possible. In the event that CT/MRI of the abdomen and the pelvis has been performed within 28 days from the date of inclusion, imaging does not need to be repeated. Further imaging examinations with CT, MRI, US, PET or CT-PET may be performed whenever considered clinically indicated after study entry.
- (i) EQ-5D instrument.
- (j) ≥5 mL serum and ≥5 mL plasma, stored at -70°C or colder. The baseline sample is preferentially drawn when the patient is on imatinib. Research serum and plasma are collected also at the time of tumour recurrence.

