3.5.4 Laboratory assessments and physical examination

3.5.4.1 Laboratory evaluations

Laboratory analyses will be carried out according to the Visit Schedule. Laboratory values will be recorded on the Follow-up Form (circle the correct range) even when normal.

Haematology

Haematology includes assessment of haemoglobin, total WBC count, platelet count, and a differential count including neutrophils, lymphocytes, monocytes, eosinophils and basophils.

Biochemistry

Biochemistry includes serum or plasma creatinine; serum albumin, total protein, total bilirubin, alkaline phosphatase, AST (SGOT), ALT (SGPT). Lactate dehydrogenase (LDH), and magnesium, calcium and phosphate (Pi) will be performed at 2 months and 5 months on study.

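### Two schedule contradictions to reconcile: electrolytes have no on-imatinib baseline or month-8 value, and follow-up of imatinib side effects is promised but not scheduled

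*Protocol*

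**What the plan says.** **Electrolytes.** The exploratory assessments in the synopsis set out a comparison of blood counts, transaminases, creatinine and "electrolytes between the baseline values measured on imatinib and the values measured at 2, 5 and 8 months after stopping imatinib". Section 2 repeats the aim in general terms and takes the screening examination as the on-imatinib baseline. Two places fix when the assays are done. Table 1, footnote (g), puts "LDH, albumin, calcium, magnesium and phosphate at follow-up months 2 and 5". Section 3.5.4.1 agrees: "magnesium, calcium and phosphate (Pi) will be performed at 2 months and 5 months on study".

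**Adverse events.** Section 3.5.6 says that imatinib side effects present before entry go on the CRF, and that "the study patients will be monitored for persistence/disappearance of the adverse effects during the study". In Table 1 the adverse-event row has an entry at screening and nothing after it. Footnote (d) defines the item as "Adverse events of imatinib at the time of study entry". Section 3.5.7 says that CRF reporting after stopping follows the visit schedule, and also that a CRF is completed at every visit while the patient is on study.

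**The concern.** A change from baseline needs a baseline. If the on-imatinib electrolyte values are not measured before the drug is stopped, no later analysis decision can replace them, and the loss occurs patient by patient as the trial enrols. A statistical analysis plan cannot repair it.

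The adverse-event conflict is of another kind. The protocol makes a commitment in one section and gives sites a schedule that does not carry it out. Section 3.5.8 names the disappearance of side effects as a benefit to the patient, and the hypothesis in section 1.5 includes remission free of them. A site that works from Table 1 would record the side effects at entry and have no scheduled item to show whether they resolved. A site that works from section 3.5.6 would try to record it. The data would then differ between centres for reasons unrelated to the patients.

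**Working it through.** No sample size, power or error rate bears on this point. The check sets the time points that each planned use of the data needs against those that Table 1, its footnotes and section 3.5.4.1 provide.

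**Laboratory comparisons (synopsis: baseline, months 2, 5 and 8)**

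| Laboratory family | Baseline | Month 2 | Month 5 | Month 8 | Contrasts with baseline possible |
|---|---|---|---|---|---|
| Blood counts | yes | yes | yes | yes | 3 of 3 |
| Transaminases (ALT, AST) | yes | yes | yes | yes | 3 of 3 |
| Creatinine | yes | yes | yes | yes | 3 of 3 |
| Calcium, magnesium, phosphate | no | yes | yes | no | 0 of 3 |

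The first three rows follow from the haematology and biochemistry rows of Table 1, which have a screening entry and a mark at every visit, and from footnotes (f) and (g). The last row follows from footnote (g) and section 3.5.4.1, which agree with each other, so a slip in one place is an unlikely explanation.

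Electrolyte time points scheduled: 2 of 4. Each of the 3 contrasts (month 2, 5 or 8 minus baseline) needs the baseline value, so 3 − 3 = 0 remain. Sodium and potassium are in neither panel, so no other electrolyte can stand in.

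Sensitivity to reading: suppose the footnote is taken to restrict follow-up only, with a baseline assay understood. The month-2 and month-5 contrasts then become possible and month 8 is still missing, giving 2 of 3. The contradiction remains under either reading.

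**Adverse events**

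| Source | Collection after stopping imatinib |
|---|---|
| Section 3.5.6 | Promised; no visits named |
| Table 1, adverse-event row | Marked at 0 of 14 follow-up visits (months 2 to 60) |
| Table 1, footnote (d) | Study entry only |
| Section 3.5.7 | CRF at every visit, with content according to the schedule; its list of necessary assessments omits adverse events |
| Appendix I, monitoring plan | Adverse events verified against source in 20% of patients; no time points given |

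The blank cells are unlikely to be a fault of table extraction, because footnote (d) gives the same limit in words. The monitoring plan does not settle the conflict: verification in 20% of patients fits entry-only collection as well as repeated collection.

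**The case against.** The best case on the other side is that little is lost. Three of the four laboratory families can be compared exactly as planned. EQ-5D, a named secondary endpoint, has a baseline and seven follow-up assessments (months 5, 11, 19, 27, 36, 48 and 60). Everything affected is exploratory or descriptive. This stands, and it limits the weight of the point. It does not restore the electrolyte baseline, and EQ-5D is a generic instrument that does not record individual side effects. Serum stored at baseline under footnote (j) might allow a later assay, but none is planned.

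A reader might infer more than the text supports:

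- **That the trial will have no adverse-event data after stopping.** This assumes that Table 1 overrides section 3.5.6. Section 3.5.6 itself commits to follow-up, section 3.5.7 requires a CRF at every visit, and the content of that form is not shown. No before/after analysis of adverse events appears among the endpoints, the objectives or section 8.3.
- **That new events after stopping should be captured.** Section 3.5.6 regards toxicity reporting as not relevant without a study drug and commits only to following existing imatinib effects. Asking for new events would add an aim, not reconcile the text.
- **That creatinine kinase is an unscheduled endpoint.** The synopsis end-point list still reads "serum transaminases, electrolytes, creatinine, creatinine kinase", but the version log records its deletion from the synopsis at V3.0, and neither the detailed comparison nor either panel includes it. It is most plausibly a leftover word.
- **That numeric laboratory results are lost.** Section 3.5.4.1 says "Laboratory values will be recorded on the Follow-up Form (circle the correct range) even when normal". The sentence says that values are recorded, and the parenthesis cannot be interpreted without the form.
- **That relief from side effects is the main benefit claimed.** The rationale also names durable remission, possible cure and cost.

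**Conclusion.** Two internal contradictions hold and should be reconciled.

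(a) Electrolytes: with the schedule followed as written, 0 of the 3 planned contrasts can be computed, because the on-imatinib baseline is absent; month 8 is absent too. This affects one of the four laboratory families in the planned comparison. It assumes that footnote (g) and section 3.5.4.1 mean what they say about timing; on the lenient reading shown above, one contrast of three is still lost.

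(b) Adverse events: section 3.5.6 conflicts with Table 1 and footnote (d). The finding is that the passages disagree and that sites cannot tell which governs. It does not show that no data will exist.

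Both matters touch exploratory or descriptive results only. The primary progression-free survival analysis, overall survival, EQ-5D and the interim rule are unaffected.

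**What to change.** **Electrolytes.** Name the electrolytes in the endpoint. Then either add them to the baseline and month-8 blood draws already in Table 1, changing footnote (g) and section 3.5.4.1 to match, or remove electrolytes from the endpoint. The first option costs a few routine assays and an edit to Table 1 and the CRF; the second costs only the edit. No new visit or blood draw is needed. In the same edit, align albumin, which footnote (g) places at months 2 and 5 and section 3.5.4.1 places in the general panel, and delete the leftover creatinine kinase.

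**Adverse events.** Either mark follow-up of the imatinib side effects recorded at entry, graded by CTCAE v4.0, at existing follow-up visits in Table 1 and reword footnote (d), or withdraw the monitoring statement from section 3.5.6. The first option costs a few minutes per visit and a CRF item; the second costs one sentence, and the protocol then no longer promises to describe whether those effects resolve.

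The electrolyte change is the more urgent, because each patient who stops imatinib without the assay has no baseline that can be measured afresh later.

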3.5.7 Patient safety and event reporting

Feasibility and adherence to the discontinuation of imatinib will be reported for all trial subjects. Each GIST patient must be carefully monitored during the course of the protocol. Necessary assessments will include physical examinations, vital signs (systolic/diastolic blood pressure and pulse rate), clinical laboratory tests (haematology, blood biochemistry), and CT/MRI evaluations. CRF reporting after discontinuation of imatinib will be conducted according to the visit schedule. A CRF has to be completed at all visits for the time period the patient is on study after discontinuation of imatinib.

Since there is now study drug in the trial, SAEs related to a study drug cannot be reported.

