8.5 Quality of Life

The QoL analyses will be done as described in 3.5.5 (http://www.euroqol.org/).

9 Notable scales

NCI/NIH Common Terminology Criteria for Adverse Events (CTCAE) v. 4.0, see http://ctep.cancer.gov/protocolDevelopment/electronic_applications/ctc.htm.

Eastern Cooperative Oncology Group performance status scale Grade Description

- **0** Fully active, able to carry on all pre-disease activities without restriction.
- 1 Restricted in physically strenuous activity but ambulatory and able to carry out work of a light or sedentary nature e.g. light housework, office work.
- 2 Ambulatory and capable of all self-care but unable to carry out any work activities. Up and about more than 50% of waking hours.
- 3 Capable of only limited self-care, confined to bed or chair more than 50% of waking hours.
- 4 Completely disabled. Cannot carry on any self-care. Totally confined to bed or chair.
- 5 Dead

10 Publication policy and authorship

The final publication will be written by the principal investigator(s). An effort will be made to include every investigator who has entered eligible study patients as a co-author, who have participated in analysis of the study data, in drafting of the manuscript, and who can assume responsibility of the study report, if the space allows. A small number of accrued patients may suffice for authorship if the space allows, and provided that the investigator has significantly contributed to acquisition of data and drafting of the manuscript.

The number of patients entered will be the major determinant of the sequence of co-authors. The study statistician, surgeons, and person(s) responsible for translational analyses may also be included as a co-author. All investigators who have included an eligible patient in the study will be acknowledged. Investigators participating in this multicentre study agree not to present data gathered from one centre or a small group of centres before the full publication, unless formally agreed to by all other investigators.

The results of this study may be published as one or more publications and presented at scientific meetings. The final report will be published. The Safety Analysis report and results of analyses of tissue or serum biological variables may be published provided that the Study Steering Committee considers their publication to be valuable to the scientific community and/or to advance management of GIST.

11 Procedures and instructions

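### After imatinib is stopped, adverse-event follow-up covers only effects listed before entry; new non-fatal clinical events and non-drug serious events have no recording rule, so comparison with entry favours stopping

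*Protocol*

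**What the plan says.** Section 3.5.6 opens with the position that "As there is no study drug, toxicity reporting is not relevant to the study". It then sets a limited collection rule: "The adverse effects related to imatinib prior to study entry will be collected on the CRFs", and after entry "the study patients will be monitored for persistence/disappearance of the adverse effects during the study". Its next paragraph is about grading: "As far as possible, adverse event grade 1-4 will be described by the NCI/NIH Common Terminology Criteria for Adverse Events". That paragraph is worded generally but does not say which events are collected or when.

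Table 1 marks its adverse-events row at screening and at none of the follow-up visits. Footnote (d) to the table describes the content of the row as "Adverse events of imatinib at the time of study entry".

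Section 3.5.7 requires a CRF at every visit after stopping but names no adverse-event item on it. On serious events it says only that "SAEs related to a study drug cannot be reported". Section 3.5.4.2 adds that "Data on concomitant diseases will not be captured on the CRFs".

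Two other places assume that adverse-event data exist. The monitoring plan in Appendix I lists adverse events for source verification in 20% of patients. Section 10 states that "The Safety Analysis report and results of analyses of tissue or serum biological variables may be published", subject to the steering committee's view of their value.

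**The concern.** Relief from imatinib side effects is part of the case for the strategy. The hypothesis at the end of section 1.5 is durable remission without those effects, and section 3.5.8 tells the reader to expect them to go once the drug is stopped. The follow-up rule in 3.5.6 can confirm this expectation but is poorly placed to contradict it: it tracks items on a list closed at entry and has no place for a symptom that first appears afterwards.

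The safety account of stopping is at stake. A report built on these data could show side effects resolving and say nothing about new non-fatal clinical events or hospitalisations, because nobody was asked to record them. No analysis plan can recover events that were not collected.

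**Working it through.** **1. Which events have a route onto the CRF after stopping?**

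| Event after stopping | Where the protocol provides for it | Recorded? |
|---|---|---|
| Death, any cause | 3.4.2 (discontinuation reason); PFS and OS in 8.3 | Yes |
| GIST progression | 3.4.2; PFS in 8.1 and 8.3 | Yes |
| Laboratory abnormality | 3.5.4.1 (Follow-up Form, by range) | Yes |
| Change in ECOG status or weight | Table 1; 3.5.4.3 | Yes |
| Pre-entry imatinib effect, present or gone | 3.5.6 | Promised in 3.5.6, not scheduled in Table 1 |
| New non-fatal clinical event | No section | No rule |
| Non-fatal serious event not related to a drug | 3.5.7 is silent | No rule |

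The fifth row is a direct conflict. Section 3.5.6 promises monitoring during the study; Table 1 and footnote (d) place adverse events at entry only.

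**2. Direction of the bias.** In the same patients, let B be the number of listed effects at entry, P the number of those still present at a later visit, and N the number of new effects present at that visit.

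- Recorded change = P − B. Since P cannot exceed B, this is zero or negative.
- True change = P + N − B.
- Recorded minus true = −N.

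The error is zero only if there are no new effects; otherwise it favours stopping. The result concerns the number of effects. It does not bind severity: a persisting effect may rise in grade, and 3.5.6 does refer to CTCAE grades.

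**3. Possible size.** The protocol states no adverse-event rate after stopping, so there is no figure of its own to reproduce. Take N = 31 (section 8.1), treat patients as independent and all followed, and assume an incidence q of at least one new event per patient. The expected number of patients affected is 31q, and the chance of at least one is 1 − (1 − q)^31.

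| Assumed q | Expected patients (of 31) | Chance of at least one |
|---|---|---|
| 2% | 0.62 | 47% |
| 5% | 1.55 | 80% |
| 10% | 3.1 | 96% |
| 20% | 6.2 | 99.9% |

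On a list closed at entry, the recorded number of new events is 0 in every row.

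A clean result would also be informative if collected. With no non-fatal serious event in 31 patients, the upper one-sided 95% limit on the risk would be 1 − 0.05^(1/31) = 9.2%. Without a collection rule, an absence of such events in the data cannot support that statement.

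**The case against.** The strongest reply is that much harm is captured. Deaths, including intercurrent ones, and progressions are recorded with their circumstances and enter PFS and OS. Laboratory values are recorded even when normal, performance status and weight are taken at each visit, and a CRF is completed each time. The grading paragraph in 3.5.6 is not confined to pre-entry effects and includes grade 5. A hospitalisation caused by recurrence may fall after progression, which is itself the primary event and a reason for leaving the study. No adverse-event measure is an endpoint, and summaries of such data often sit in the SAP, which is not at hand.

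Most of this stands, and it rules out several stronger readings:

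- A reader might infer that new or serious events are never counted. The documents do not support that: fatal events, progressions and laboratory changes are counted.
- A reader might infer that the adverse-event burden can only fall. That holds for the number of listed effects (fall or stay equal), not for the grade of one that persists.
- A reader might take 3.5.7 as excluding all serious events. It rules out only drug-related ones and does not address the rest, which is a gap rather than an exclusion.
- A reader might infer that a specific prevalence will be misreported. The protocol plans no such figure, and onset rates after stopping would have to be assumed.

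The gap itself remains. A grading scale does not define which events to collect, a CRF with no named adverse-event item does not create one, and the scope of collection is protocol and CRF content that a later SAP cannot repair.

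**Conclusion.** The point holds in limited form. After imatinib is stopped, the protocol describes adverse-event follow-up only for effects from before entry, and Table 1 does not schedule even that. New non-fatal clinical events and non-drug serious events have no recording rule. Any comparison of the number of adverse effects with entry is therefore biased towards improvement, by exactly the number of new effects.

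The direction follows from the text alone. The size is unknown: at an assumed incidence of 5% to 10%, between 1.55 and 3.1 of 31 patients would have an event that the list does not hold. This assumes that sites record what the protocol describes and no more; a CRF that asks more widely would shrink the problem, but the protocol does not call for one. The primary PFS analysis and overall survival are untouched. The change should be made, because the data cannot be recovered later, but the trial's main conclusion does not depend on it.

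**What to change.** - **Section 3.5.6:** replace the present follow-up rule. At each scheduled visit, record the adverse events present by CTCAE v4.0 grade and classify each as persisting, worsened or new since stopping. Use events ongoing at entry as the reference, so that effects that resolved earlier in treatment are not part of the comparison.
- **Section 3.5.7:** record serious events after stopping, including hospitalisations, whatever their relation to a drug.
- **Table 1:** mark the adverse-events row at the follow-up visits and reword footnote (d) to match.
- **Appendix I and section 10:** bring the adverse-event verification item and the Safety Analysis report into line with what is collected.

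The cost is modest but not nil. No visit or test is added. Table 1 has 14 visits after entry, so one extra page per visit is at most 14 × 31 = 434 paper CRF pages, fewer as patients progress or leave, plus some monitoring. The change needs a protocol amendment with ethics approval and, where relevant, approval by the authorities (section 11.1.1). The side-effect benefit of stopping may also look less favourable than under the present rule.
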